12.2.9 Populations Used in Analyses

The main immunogenicity analyses will be performed on the PPAS analysis set including PPAS2 for the primary objective and PPAS1 for secondary objective 1, and will be confirmed on the FAS2 and FAS1. In the FAS1 and FAS2, subjects will be analyzed by the vaccine group to which they were randomized.

The safety analysis will be performed on the SafAS, SafAS1 to SafAS 4. Subjects will be analyzed according to the vaccine they actually received.

12.3 Handling of Missing Data and Outliers

12.3.1 Safety

No replacement will be done.

12.3.2 Immunogenicity

Missing data will not be imputed. No test or search for outliers will be performed.

In order to appropriately manage extreme values (undetectable responses < LLOQ and \geq upper limit of quantitation [ULOQ]), the following computational rule is applied to the values provided in the clinical database for each blood sample drawn for analysis purposes:

- If a value is < LLOQ, then use the computed value LLOQ/2
- If a value is between \geq LLOQ and < ULOQ, then use the value
- If a value is \geq ULOQ, then use the computed value ULOQ

The derived endpoint of fold-rise is computed as follows:

- Calculate the fold-rise of values as the ratio of post-baseline computed value divided by baseline computed value

If baseline or post baseline value is missing, then the vaccine seroresponse is missing.

12.4 Interim / Preliminary Analysis

No interim analyses are planned.

12.5 Determination of Sample Size and Power Calculation

Approximately a total of 1652 subjects will be enrolled.

For the Primary Objective

With 716 enrolled subjects in Group 1 and in Group 2, the study will have 96.2% power to declare the non-inferiority of Group 1 versus Group 2 based on A, C, W, Y hSBA antibody titers (ratio of GMTs in the 2 groups) after a 3-dose series to infants and toddlers 6 weeks to 18 months old, assuming:

- An estimated 26.2% dropout rate from the PPAS (528 subjects evaluable by group),
- a 1-sided alpha level of 2.5%,
- a non-inferiority margin of 1.5 (GMT ratio),
- a standard deviation (SD) of log10-transformed titers of 0.7 for serogroups A and C, 0.5 for serogroup Y, and 0.6 for serogroup W.

Table 12.1: Power of the study based on the primary objective

Antigen	MenACYW Standard Deviation*	Non-inferiority Margin	Power
A	0.7	1.5	98.3%
C	0.7	1.5	98.3%
Y	0.5	1.5	> 99.9%
W	0.6	1.5	99.7%
Overall			96.2%

Since the hypothesis needs to be met for all serogroups, no alpha adjustment for multiple comparisons is necessary in these calculations.

* SDs are based on the results of the MET39 (NCT01049035) MenACYW 2/4/12 months schedule (Group 3) after booster results. For the power computation, the same SD in the control group (Nimenrix®) is assumed.

For the Secondary Objective

With 716 enrolled subjects in Group 1 and in Group 2, the study will have a > 90% power (Farrington and Manning formula) to declare the non-inferiority of Group 1 versus Group 2 based on A, C, W, Y hSBA antibody titers $\geq 1:8$ (difference in the percentage of seroprotected subjects in the 2 groups) after 2 doses in infancy at 2 months and 4 months of age, assuming:

- An estimated 26.2% dropout rate from the PPAS (528 subjects evaluable per group)
- A 1-sided alpha level of 2.5%,
- A non-inferiority margin of 10% (percentage difference)

Table 12.2: Power of the study for the secondary objective

Antigen	Estimated Percentage of hSBA Titer $\geq 1:8$ Nimenrix®*	Non-inferiority margin†	Power
A	76%	10%	96.7%
C	94%	10%	> 99.9%
Y	71%	10%	94.7%
W	82%	10%	98.7%
Overall			90%

Since the hypothesis needs to be met for all serogroups, and the secondary objective is to be tested only if the primary objective succeeds, no alpha adjustment for multiple comparisons is necessary in these calculations.

* Percentages of subjects with an hSBA titer $\geq 1:8$ are based on the MET39 (NCT01049035) MenACYW 2/4/12 months schedule (Group 3) post dose 2 results using estimates 2% lower than in the MenACYW group. The power is calculated with the assumption that the estimates from the investigational group equal that of the control group corresponding to the estimated percentages in the Nimenrix® group described above.

† A non-inferiority margin of 10% has been widely used in previous studies evaluating the same antigens and in a competitor's study of the same type. Also taking into account the level of the reference rate taken in the Nimenrix® group, it is reasonable to use 10%.

The sample size has been arbitrarily set to 110 subjects in Group 3 and Group 4 as these data are not intended to be used for any hypothesis testing. No formal sample size calculations were performed. In each group, there is more than 95% probability to observe an event with an incidence of 2.7%.

In case of unexpected situation or any study hold resulting in an unexpected number of unevaluable subjects, total sample size may be increased to replace withdrawn, or unevaluable subjects.

13 Ethical and Legal Issues and Investigator / Sponsor Responsibilities

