With 716 enrolled subjects in Group 1 and in Group 2, the study will have a > 90% power (Farrington and Manning formula) to declare the non-inferiority of Group 1 versus Group 2 based on A, C, W, Y hSBA antibody titers $\geq 1:8$ (difference in the percentage of seroprotected subjects in the 2 groups) after 2 doses in infancy at 2 months and 4 months of age, assuming:

- An estimated 26.2% dropout rate from the PPAS (528 subjects evaluable per group)
- A 1-sided alpha level of 2.5%,
- A non-inferiority margin of 10% (percentage difference)

Table S2: Power of the study for the secondary objective

Antigen	Estimated Percentage of hSBA Titer $\geq 1:8$ Nimenrix®*	Non-inferiority margin†	Power
A	76%	10%	96.7%
C	94%	10%	> 99.9%
Y	71%	10%	94.7%
W	82%	10%	98.7%
Overall			90%

Since the hypothesis needs to be met for all serogroups, and the secondary objective is to be tested only if the primary objective succeeds, no alpha adjustment for multiple comparisons is necessary in these calculations.

* Percentages of subjects with an hSBA titer $\geq 1:8$ are based on the MET39 (NCT01049035) MenACYW 2/4/12 months schedule (Group 3) post dose 2 results using estimates 2% lower than in the MenACYW group. The power is calculated with the assumption that the estimates from the investigational group equal that of the control group corresponding to the estimated percentages in the Nimenrix® group described above.

† A non-inferiority margin of 10% has been widely used in previous studies evaluating the same antigens and in a competitor's study of the same type. Also taking into account the level of the reference rate taken in the Nimenrix® group, it is reasonable to use 10%.

The sample size has been arbitrarily set to 110 subjects in Group 3 and Group 4 as these data are not intended to be used for any hypothesis testing. No formal sample size calculations were performed. In each group, there is more than 95% probability to observe an event with an incidence of 2.7%.

In case of unexpected situation or any study hold resulting in an unexpected number of unevaluable subjects, total sample size may be increased to replace withdrawn, or unevaluable subjects.

Table of Study Procedures - Groups 1, 2, and 3

Phase III study, 5 visits, 3 vaccination visits, 4 telephone calls, 10 vaccine injections, 4 blood collections per subject,
11- to 17-month duration per subject

Visit/Contact	Visit 1	Telephone Call (TC) 1	Visit 2	TC2	Visit 3	TC3	Visit 4	TC4	Visit 5

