1.2.1.1 Study MET39 (Phase II)

MET39 was a Phase II, randomized, open-label, multi-center study conducted in the US for which 580 healthy subjects from 2 to 15 months of age were enrolled. This study evaluated the optimal vaccination schedule in the infant/toddler population. Subjects in Group 1 through Group 4 received 1, 2, or 3 primary doses plus an additional dose of the MenACYW conjugate vaccine in the second year of life, concomitantly with routine pediatric vaccines at several different vaccination schedules. Subjects in Group 5 received 1 dose of the MenACYW conjugate

^a Countries under centralized procedure include Austria, Belgium, Bulgaria, Croatia, Cyprus, Czech Republic, Denmark, Estonia, Finland, France, Germany, Greece, Hungary, Ireland, Italy, Latvia, Lithuania, Luxembourg, Malta, Netherlands, Poland, Portugal, Romania, Slovakia, Slovenia, Spain, and Sweden, United Kingdom (Northern Ireland) (remaining part after Brexit) and other European Economic Area countries – Iceland, Liechtenstein, and Norway.

vaccine concomitantly with routine pediatric vaccines. The routine pediatric vaccines administered concomitantly with MenACYW conjugate vaccine at various schedules included Prevnar® (pneumococcal 7-valent conjugate vaccine) or Prevnar 13® (pneumococcal 13-valent conjugate vaccine [PCV13]), Pentacel® (diphtheria, tetanus, pertussis [acellular, component]-poliovirus [inactivated]//*Haemophilus influenzae* type b [DTaP-IPV//Hib]), ROTARIX® (monovalent rotavirus vaccine [RV1]) or RotaTeq® (pentavalent rotavirus vaccine [RV5]), hepatitis B [HB] vaccine, M-M-R® II vaccine (measles, mumps, and rubella vaccine [MMR]), and VARIVAX® (varicella vaccine).

Immunogenicity

After the primary series consisting of 1, 2, or 3 doses of MenACYW conjugate vaccine, protective serum bactericidal assay using human complement (hSBA) threshold titers of $\geq 1:8$ were attained by $> 88\%$ of subjects for serogroup C and by 62% to 74% for serogroup A. For serogroups Y and W, $\geq 90\%$ achieved the threshold titer after 3 doses, 75% to 84% after 2 doses, but only 25% after a single dose administered at 6 months of age.

After an additional dose of MenACYW conjugate vaccine in the second year of life (12 or 15 months), between 91% and 100% of the subjects achieved the protective threshold regardless of the number of doses they received in the first year of life.

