5.5 Determination of Sample Size and Power Calculation

Approximately a total of 1652 subjects was planned to be enrolled.

For the Primary Objective

With 716 enrolled subjects in Group 1 and in Group 2, the study will have 96.2% power to declare the non-inferiority of Group 1 versus Group 2 based on A, C, W, Y hSBA antibody titers (ratio of GMTs in the 2 groups) after a 3-dose series to infants and toddlers 6 weeks to 18 months old, assuming:

- An estimated 26.2% dropout rate from the PPAS (528 subjects evaluable by group),
- a 1-sided alpha level of 2.5%,

- a non-inferiority margin of 1.5 (GMT ratio),
- a standard deviation (SD) of log10-transformed titers of 0.7 for serogroups A and C, 0.5 for serogroup Y, and 0.6 for serogroup W.

The calculated power for the primary objective of the study using those parameters is presented in the [Table 5.2](#) below.

Table 5.2: Power of the study based on the primary objective

Antigen	MenACYW Standard Deviation*	Non-inferiority Margin	Power
A	0.7	1.5	98.3%
C	0.7	1.5	98.3%
Y	0.5	1.5	> 99.9%
W	0.6	1.5	99.7%
Overall			96.2%

Since the hypothesis needs to be met for all serogroups, no alpha adjustment for multiple comparisons is necessary in these calculations.

* SDs are based on the results of the MET39 (NCT01049035) MenACYW 2/4/12 months schedule (Group 3) after booster results. For the power computation, the same SD in the control group (Nimenrix®) is assumed.

For the Secondary Objective

With 716 enrolled subjects in Group 1 and in Group 2, the study will have a > 90% power (Farrington and Manning formula) to declare the non-inferiority of Group 1 versus Group 2 based on A, C, W, Y hSBA antibody titers $\geq 1:8$ (difference in the percentage of seroprotected subjects in the 2 groups) after 2 doses in infancy at 2 months and 4 months of age, assuming:

- An estimated 26.2% dropout rate from the PPAS (528 subjects evaluable per group)
- A 1-sided alpha level of 2.5%,
- A non-inferiority margin of 10% (percentage difference)

The calculated power for the secondary objective of the study using those parameters is presented in the [Table 5.3](#) below.

Table 5.3: Power of the study for the secondary objective

Antigen	Estimated Percentage of hSBA Titer $\geq 1:8$ Nimenrix®*	Non-inferiority margin†	Power
A	76%	10%	96.7%
C	94%	10%	> 99.9%
Y	71%	10%	94.7%
W	82%	10%	98.7%
Overall			90%

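### The serogroup A (76%) and Y (71%) rates behind the Secondary Objective 1 power do not agree with the protocol's own summary of MET39

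*Protocol*

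**What the plan says.** Secondary Objective 1 tests non-inferiority of Group 1 to Group 2 on the percentage with hSBA titre of at least 1:8, 30 days after the second infant dose. The margin is 10 percentage points, and all four serogroups must pass (Protocol 12.1.2.1 and 12.1.2.2). It is tested only if the primary objective is met.

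Table 12.2 in Protocol 12.5 assumes Nimenrix rates of A 76%, C 94%, Y 71% and W 82%. It gives powers of 96.7%, above 99.9%, 94.7% and 98.7%, with 90% overall; the text above the table claims more than 90%. The footnote describes the rates as "based on the MET39 (NCT01049035) MenACYW 2/4/12 months schedule (Group 3) post dose 2 results using estimates 2% lower than in the MenACYW group" and adds: "The power is calculated with the assumption that the estimates from the investigational group equal that of the control group". The same rates and powers appear in the synopsis ("Table S2: Power of the study for the secondary objective") and in SAP 5.5 ("Table 5.3: Power of the study for the secondary objective").

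Protocol 1.2.1.1 summarises the same study at the same threshold. "After the primary series consisting of 1, 2, or 3 doses of MenACYW conjugate vaccine", the threshold was reached by more than 88% for serogroup C and "by 62% to 74% for serogroup A". For Y and W it gives "75% to 84% after 2 doses".

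**The concern.** The 2/4/12-month schedule has a two-dose primary series. Its post-dose-2 rates should therefore lie inside the Section 1.2.1.1 range for A, which spans series of 1, 2 and 3 doses, and inside the two-dose range for Y and W. The rates implied by the footnote do so for C and W but not for A or Y.

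At stake is the planning power of a formally tested, gated objective that needs all four serogroups. The overall figure from the tabled inputs is only about half a point above 90%, so changes of a few points in A and Y decide whether the claim of more than 90% holds. The footnote also cites the level of the reference rate in support of the 10% margin, so those rates ought to be traceable.

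**Working it through.** **Inputs** (Protocol 12.5): 716 enrolled per group, 26.2% dropout, 716 × 0.738 = 528.4, so n = 528 per arm; margin 0.10; one-sided alpha 0.025; equal true rates in both arms.

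**Formula.** Farrington-Manning: power = Φ[(p₁ − p₂ + 0.10 − 1.96·s₀)/s₁]. Here s₁² = [p₁(1−p₁) + p₂(1−p₂)]/n, and s₀² has the same form at the maximum-likelihood rates restricted to p₁ − p₂ = −0.10. Overall power is the product of the four, which assumes independent serogroups.

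**Reproducing the table.** For A at 76%, the restricted rates are 0.7031 and 0.8031, s₀ = 0.0264 and s₁ = 0.0263. The argument is 1.839 and the power 96.7%.

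| Serogroup | Rate | Stated power | Recomputed |
|---|---|---|---|
| A | 76% | 96.7% | 96.7% |
| C | 94% | > 99.9% | > 99.9% |
| Y | 71% | 94.7% | 94.8% |
| W | 82% | 98.7% | 98.8% |
| Overall | | 90% | 90.5% |

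The unpooled formula and a simulation of the planned Wilson score interval agree closely. The arithmetic is sound.

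**Comparing the inputs** (tabled rate plus 2 points):

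| Serogroup | Implied MET39 rate | Section 1.2.1.1 | Consistent? |
|---|---|---|---|
| A | 78% | 62% to 74% (1, 2 or 3 doses) | No, 4 points above |
| C | 96% | > 88% | Yes |
| Y | 73% | 75% to 84% (2 doses) | No, 2 points below |
| W | 84% | 75% to 84% (2 doses) | Yes |

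Reading the 2% as relative gives A 76/0.98 = 77.6% and Y 71/0.98 = 72.4%. Ignoring it leaves 76% and 71%. All of these remain outside the ranges, and the gaps are too large for rounding.

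**Power if Section 1.2.1.1 is right.** Subtracting 2 points from its ranges gives A 60% to 72% and Y 73% to 82%:

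- A: 91.4% to 95.2% (stated 96.7%)
- Y: 95.5% to 98.8% (stated 94.7%)

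A relative 2% changes little: A 91.6% to 95.4%, Y 95.7% to 98.8%.

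**Overall, with C and W as tabled:**

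| A | Y | Independence | Correlation 0.3 (assumed) |
|---|---|---|---|
| 72% | 73% | 89.8% | 90.5% |
| 72% | 75% | 90.5% | 91.1% |
| 72% | 82% | 92.8% | 93.2% |
| 60% | 73% | 86.2% | 87.1% |
| 60% | 82% | 89.1% | 89.6% |

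For 90% overall under independence, the assumed A rate must be at least 72.6% if Y is 73%, 70.6% if Y is 75%, and 63.6% if Y is 82%.

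**The case against.** The strongest reply concerns weight. Nothing in the margin, interval method, decision rule, gatekeeping, enrolment or primary power changes. The SAP is written largely in the past tense, so restated power cannot alter the design. At the nearest consistent rates the overall is 89.8%, which still rounds to the tabled 90%; at A 72% and Y 75% it equals the 90.5% from the tabled inputs. The 86.2% end needs 62% to be the two-dose result for A and Y to sit at its lowest too, and the text does not say that 62% is a two-dose figure. Independence and equal rates are both cautious: if MenACYW truly were 2 points better than Nimenrix (the table's own offset, unproven), overall power would be about 97% to 99% over the whole range.

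A different MET39 analysis set could also explain gaps of 2 to 4 points. Section 1.2.1.1 does not report Group 3 separately, and part of the MET39 account is missing from the text available here.

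The points on size stand: the effect is modest and the sample size is not shown to be inadequate. They do not remove the conflict. No available text mentions a different analysis set, and further MET39 detail could not place 78% inside 62% to 74% as written.

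**Conclusion.** The concern holds. The A and Y powers for Secondary Objective 1 rest on rates that the protocol's own summary of the source study contradicts, under every reading of the 2% offset. That the two passages disagree is certain; which one is wrong is not. If Section 1.2.1.1 is right, A's power is overstated by 1.5 to 5.3 points (96.7 − 95.2; 96.7 − 91.4) and Y's is understated by 0.8 to 4.1 points (95.5 − 94.7; 98.8 − 94.7).

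The overall figure would then lie between 86.2% and 92.8% under independence, against 90.5% from the tabled inputs. The low end depends on the unsupported assignment of 62% to the two-dose schedule. These results assume C and W as tabled, equal true rates in the two arms and 528 evaluable per arm. This should be corrected, but it does not threaten the trial's conclusions.

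**What to change.** Look up the MET39 Group 3 post-dose-2 percentages for each serogroup and state them beside the table, with the analysis set and whether the 2% is in points or relative. Then correct the passage that is wrong: either Table S2, Table 12.2 and SAP Table 5.3, or the sentences in Section 1.2.1.1. Restate the serogroup and overall powers from the verified rates. A note that the overall figure assumes independent serogroups would help but is optional.

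Exchanging the A and Y rows (A 71%, Y 76%) would imply MET39 rates of 73% and 78%, which fit both ranges and leave the overall at 90.5%. A transcription slip is therefore possible, but the documents do not confirm it, so no replacement values should be entered before the check.

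The cost is one look-up, then two rows in three tables or an edit to Section 1.2.1.1, and possibly one overall figure. The restated overall power may be slightly lower or higher than now.

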13.1 Ethical Conduct of the Study / Good Clinical Practice

The conduct of this study will be consistent with the standards established by the Declaration of Helsinki and compliant with the ICH guidelines for GCP as well as with all local and / or national regulations and directives.

13.2 Source Data and Source Documents

“Source data” are the data contained in source documents. Source documents are original documents or certified copies, and include, but are not limited to, diary cards, medical and hospital records, screening logs, informed consent / assent forms, telephone contact logs, and worksheets. The purpose of study source documents is to document the existence of subjects and to substantiate the integrity of the study data collected. Investigators must maintain source documents so that they are accurate, complete, legible, and up to date.

For missing or discrepant data on a diary card, the study coordinator will obtain verbal clarification from the subject, enter the response into the “investigator’s comment” page of the diary card, and transfer the information to the CRB.

The subject pre-screening log should list all individuals contacted by the Investigators to participate in the study, regardless of the outcome.

The Investigator must print^a any electronic records on an ongoing basis, sign and date them immediately after creation, and keep the printouts on file as source documents that can be verified by the Sponsor or an inspector against the electronic records. Any subsequent changes of an electronic record require the record to be re-printed, dated (with an indication of the date of change), and signed. Such records must also be kept together with the original printed copy.

Good Documentation Practice should be followed by the Investigator and the site staff managing source documents.

13.3 Confidentiality of Data, Data Protection and Access to Subject Records

Prior to initiation of the study, the Investigator will sign a fully executed confidentiality agreement with Sanofi Pasteur. In the event a subject’s medical records are not at the investigational site, it is the responsibility of the investigator, to obtain those records if needed.

All personal data collected related to subjects, Investigators, or any person involved in the study, which may be included in the Sponsor’s databases, shall be treated in compliance with all applicable laws and regulations, including the Global Data Protection Regulation (GDPR). Data

^a Unless the electronic medical records are managed by validated computerized systems that are compliant with US 21 CFR Part 11, in which case they are acceptable on their own.

collected must be adequate, relevant and not excessive, in relation to the purposes for which they are collected. Each category of data must be properly justified and in line with the study objective.

Subjects' race and ethnicity will be collected in this study because these data are required by regulatory agencies (eg, the FDA in the US).

Subjects will be assigned a unique identifier by the Sponsor. Any subject records or datasets that are transferred to the Sponsor will contain the identifier only; subject names or any information that would make the subject identifiable will not be transferred.

The subject must be informed that his/her personal study-related data will be used by the Sponsor in accordance with local data protection law. The level of disclosure must also be explained to the subject.

The subject must be informed that his/her medical records may be examined by Clinical Quality Assurance auditors or other authorized personnel appointed by the Sponsor, by appropriate IRB/IEC members, and by inspectors from regulatory authorities.

When archiving or processing personal data pertaining to the Investigator and/or to the subjects, the Sponsor shall take all appropriate measures to safeguard and prevent access to this data by any unauthorized third party.

13.4 Monitoring, Auditing, and Archiving

13.4.1 Monitoring

Before the start of the study (ie, before the inclusion of the first subject in the first center), the Investigators and the Sponsor's staff or a representative will meet at the site-initiation visit to discuss the study protocol and the detailed study procedures. Emphasis will be placed on inclusion and exclusion criteria, visit timing, safety procedures, informed consent procedures, SAE reporting procedures, CRB completion, and the handling of samples and products. The Sponsor's staff or a representative will ensure and document that all material to be used during the study has been received at the site; and that the study investigator team and local Sponsor/delegate staff have been properly informed about the study, GCP and regulatory requirements, and the Sponsor's procedures. Specific training sessions for the study investigator team and the CRAs on these topics may be performed as necessary, and should be documented.

The following instruction manuals will be provided: the CRF Completion Instructions for entering data into the CRB, and the Operating Guidelines for detailed study procedures such as the product management and sample-handling procedures.

After the start of the study, the Sponsor's staff or a representative will be in regular contact with the investigational team through telephone calls and regular follow-up visits. The Investigator or delegate must be available for these visits, and must allow the Sponsor/delegate staff direct access to subject medical files and CRBs. During these visits, the Sponsor/delegate staff will:

- Evaluate the quality of the study progress (adherence to protocol and any study-specific guidelines, quality of data collection and document completion, signature of consent forms, occurrence of SAEs, sample and product management, cold-chain monitoring, archiving)

- Source-verify completed CRBs and any corresponding answered queries. In exceptional situations (eg, lock down due to COVID-19) where the monitor cannot access site, and only after validation with Sponsor, the subject source data verification may be done remotely, under conditions defined in the Monitoring Plan.
- Determine the number of complete or ongoing issues identified at monitoring visits (ieg, protocol deviations, SAEs). Any identified problems will be discussed with the Investigator, and corrective or preventive actions will be determined, as appropriate.
- After all protocol procedures have been completed and the data have been entered into the CRB, the Investigator must still be available to answer any queries forwarded by the Sponsor. All data-related queries must be completed prior to database lock.

At the end of the study, a close-out visit will be performed to ensure that:

- The center has all the documents necessary for archiving
- All samples have been shipped to the appropriate laboratories
- All unused materials and products have been either destroyed or returned to the Sponsor

